### **13.1.6 Informed Consent**

The ICF will be in accordance with the Declaration of Helsinki, principles of GCP, applicable regulatory requirements, subject privacy requirements and the Sponsor's policies. The ICF must be reviewed by the Sponsor and approved by the IRB.

Each subject must provide signed informed consent according to local requirements, after the nature of the study has been fully explained, in order to participate in the study. The ICF must be signed prior to performance of any study-related activity.

The investigator, or designee, must explain to potential subjects the aims, methods, reasonably anticipated benefits, potential hazards and risks of the study, right to refuse participation and right to withdraw without affecting the subject's medical care. The other elements of the informed consent will be explained, and subjects will be given the opportunity to ask questions. After this explanation, but before entry into the study, consent should be appropriately documented by the subject's dated signature. If a subject is unable to read or requires a translator, an impartial witness must be present during the entire informed consent discussion and process. The signature of the impartial witness will certify

---

the subject's consent. The subject will be given a signed and dated copy of the informed consent form.

Subjects will not be asked prior to each visit if they want to continue to participate in the study. It will be the subject's responsibility to inform the study staff prior to a procedure if they want to be withdrawn from the study.

### **13.1.7 Investigational Product(s)**

Any investigational product (IP) under evaluation must be kept under strict control and used only as described in the protocol. The Investigator will be asked to ensure that IP(s) is stored and returned/destroyed appropriately and to provide documentation in support of this.

All IP(s) will be labeled according to regulatory requirements. IP(s) must be stored under conditions set forth by the Sponsor in this protocol, on the product label, and/or communicated in writing. The IP(s) must be installed in a segregated area of the BioLife collection centers, which are expected to maintain their standard security protocols and access restrictions throughout the duration of the study. BioLife shall establish site-specific standard operating procedures that instruct staff to only use study devices (Test and Control) for on-study collections.

If an IP(s) fails to perform in the expected manner, the Investigator will notify the Sponsor immediately.

## 15.2 IQPP Standard for Recording Donor Adverse Events

Embedded PDF	 IQPP_DAERS_V2.pdf
URL	IQPP Standard for Recording Donor Adverse Events

This is a multicenter randomized controlled clinical trial to evaluate the Aurora Xi New Nomogram for the collection of plasma. The study is to determine whether the overall rate of significant hypotensive adverse events (SHAEs) in donors using the Aurora Xi New Nomogram is less than double the rate of SHAEs in donors using the Aurora Xi Optimized Nomogram. Randomization will be carried out within blocks of variables size (2, 4, or 6) within centers. Donors will be recruited until outcomes are available for a minimum of 51,720 plasmapheresis procedures (approximately 11,519 individual donors) from three BioLife plasma centers. Donors will be randomized in a 1:1 ratio to donate in procedures under the New Nomogram (Test) or the Optimized Nomogram (Control). Donors will provide donations over an 8-week follow-up period. Subjects will be retained in the assigned study arm (Test/Control) throughout their participation in the study period.

2.1 Study Objectives

Primary Objective:

The primary objective of this study is to demonstrate that the overall rate of significant hypotensive adverse events (SHAEs, IQPP DAE Classification 1.2-1.6) in donors using the Aurora Xi New Nomogram algorithm is less than double the SHAE rate in donors using the Aurora Xi Optimized Nomogram algorithm.

Secondary Objectives:

- To determine if the incidence rate of SHAEs per donor status (first-time or repeat donor) observed with the New Nomogram (Test arm) is non-inferior to the incidence rate observed with the Optimized Nomogram (Control arm).
- To determine if the incidence rate of SHAEs for female donors observed with the New Nomogram (Test arm) is non-inferior to the incidence rate observed with the Optimized Nomogram (Control arm).
- To determine if the incidence rate of SHAEs for donors ≤ 20 years of age observed with the New Nomogram (Test arm) is non-inferior to the incidence rate observed with the Optimized Nomogram (Control arm).
- To determine if the incidence rate of SHAEs for donors weighing ≤ 124 lbs observed with the New Nomogram (Test arm) is non-inferior to the incidence rate observed with the Optimized Nomogram (Control arm).
- To determine if the incidence rate of hypotensive severe/injury adverse events (IQPP DAE Classification 1.5 or 1.6) observed with the New Nomogram (Test arm) is non-inferior to the incidence rate observed with the Optimized Nomogram (Control arm).
- To determine if the time from start of plasmapheresis procedure to the first SHAE observed with the New Nomogram (Test arm) is non-inferior to the time observed with the Optimized Nomogram (Control arm).

Exploratory Objectives:

- To compare the plasma volume collected with the New Nomogram (Test arm) versus the Optimized Nomogram (Control arm)
- To determine the collection time with the New Nomogram (Test arm)

3 Statistical Methodology

3.1 Sample Size Determination

The sample size requirement is calculated based on a model for correlated binary data in which the marginal mean is modelled with a log-link function and set by

$$\log \mu_{ij} = \beta_0 + \beta_1 X_i$$

where $X_i = 1$ for an individual assigned to the experimental arm and $X_i = 0$ otherwise. Note that center is not controlled for in the sample size calculation. Controlling for center is anticipated to improve power by explaining variation in the response, so this is a conservative approach to estimating the sample size since the power is anticipated to be at least the desired power. For the sample size derivation, the fitted model uses the identity variance function and a working independence assumption with a robust variance derived from a joint model to account for the association in the responses from serial donations from the same donor. The calculations require specification of the mean $\mu_x = E(Y_{ij}|X_i = x)$ and the variance $V_x = \text{var}(Y_{ij}|X_i = x)$ of the response Y_{ij} to procedure j from donor i as well as the within-donor correlation. If κ_x and μ_x is the mean and variance for the number of procedures for a donor in arm x and n is the total number of donors to be recruited, then the asymptotic (large sample) variance (*asvar*) of the estimator of the log relative rate satisfies

$$\text{asvar} \left\{ \sqrt{n} \left(\hat{\beta}_1 - \beta_1 \right) \right\} \simeq \frac{2V_0}{\kappa_0 \mu_0^2} \left(1 + \frac{\delta_0 \rho}{\kappa_0} \right) + \frac{2V_1}{\kappa_1 \mu_1^2} \left(1 + \frac{\delta_1 \rho}{\kappa_1} \right)$$

where $\delta_x = \nu_x + \kappa_x^2 - \kappa_x$ and ρ is the within-donor correlation in the responses over successive procedures from the same donor. The sample size involves computation of an asymptotic robust variance estimate for the estimator based on a multivariate binary probability mass function with specified marginal event rates of SHAE for the Test and Control arms and a specified exchangeable correlation for responses over successive procedures within the same donor, using the conditional linear family (Preisser and Qaqish, 2014) of multivariate binary models. In addition to the response model, a zero-truncated negative binomial model is used for the number of donation procedures over time from each donor which accommodates between-donor heterogeneity in the procedure rate. The number of required donors is computed based on the constraint

$$P \left(\hat{\beta}_1 + 1.96 \sqrt{\text{asvar}_A(\hat{\beta}_1)} < \beta_{1M} | \beta_1 = \beta_{1A} \right) = 0.80$$

which ensures that the probability that the upper limit of a two-sided 95% confidence interval for the relative risk is below $RR_M = \exp(\beta_{1M}) = 2$ with 80% power if the true log relative rate is determined by β_{1A} . Based on historical data, the event rate in the control arm is expected to be 0.221% thus setting $pc = 0.00221$ or equivalently $\log \mu_0 = \beta_0 = \log(0.00221)$. The margin of non-inferiority is specified as $\exp(\beta_{1M}) = 2$. To accommodate a slight elevation in the SHAE rate under the alternative hypothesis of non-inferiority, the sample size calculations will be carried out with $\exp(\beta_{1A}) = 1.2$, corresponding to a 20% relative increase in the SHAE rate (still within the region of non-inferiority). Accommodating a slight increase helps ensure that the power objectives are met to demonstrate non-inferiority even if there is a 20% relative increase in the SHAE rate using

the Aurora Xi New Nomogram. In order to achieve 80% power when $\exp(\beta_{1A})$ equals 1.2, when donations are taken over an 8-week follow-up period, a sample size of $n = 11,519$ donors may be required. The total number of procedures across all trial participants of $n \times \kappa$ will target 51,720 for the primary endpoint evaluation.

3.2 Analysis Populations

3.2.1 Intent-to-Treat (ITT) Analysis (All Subjects Enrolled)

The Intent-to-Treat Analysis (All Subjects Enrolled) will be based on all subjects who provided informed consent, were randomized, and had at least one procedure initiated during the study. Outcomes for all procedures will be analyzed and responses attributed to the arm to which donors were randomized.

3.2.2 Per-Protocol (PP) Analysis

The Per-Protocol Analysis will restrict attention to procedures in which the device used (Test or Control) matched the arm to which the donor was randomized.

3.3 Methods of Statistical Analysis

Summary statistics (N, mean, standard deviation, median, minimum, and maximum) will be reported on continuous (numeric) parameters for each randomization group for the Intent-to-Treat and Per-Protocol analyses unless otherwise indicated. All summary statistics will be presented at a rounded precision. Summary statistics (e.g., counts and percentages) will be reported on categorical (non-numeric) parameters for each randomization group for the Intent-to-Treat and Per-Protocol analyses unless otherwise indicated. In addition to the Secondary Endpoint analyses, summary statistics will be shown for illustrative purposes for subgroups defined by donor status, gender, age, and weight. All calculations will be performed using SAS 9.4 (Windows platform).

4 Analysis Parameters

4.1 Primary Parameter

The primary objective is to demonstrate non-inferiority of the Aurora Xi New Nomogram compared to the Aurora Xi Optimized Nomogram with respect to the occurrence of a significant hypotensive adverse event (SHAE). Let P_E denote the probability of a SHAE for a procedure using the Aurora Xi New Nomogram algorithm (where E stands for experimental) and let P_C denote the probability of a SHAE for a procedure using the Aurora Xi Optimized Nomogram algorithm (where C stands for Control). The effect of the Aurora Xi New Nomogram compared to the Aurora Xi Optimized Nomogram is expressed as a relative rate $RR = P_E/P_C$ for a SHAE. A non-inferiority margin of $RR_M = 2$ is set to define a non-inferiority region of $[0, RR_M]$ so that any relative rate less than RR_M corresponds to settings where the Aurora Xi New Nomogram is considered non-inferior to the Aurora Xi Optimized Nomogram algorithm. The corresponding hypotheses are

$$H_0 : RR \geq RR_M \text{ (inferiority)} \quad \text{vs.} \quad H_A : RR < RR_M \text{ (non-inferiority)}$$

with $RR_M = 2$ so if the null hypothesis (H_0) is rejected in favor of the alternative hypothesis (H_A) then non-inferiority is demonstrated. The test will be carried out based on the confidence interval

approach. If the upper limit of a two-sided 95% confidence interval for RR is below $RR_M = 2$, then non-inferiority will be demonstrated.

4.2 Secondary Parameters

Suppose individual i in a sample of size n provides K_i procedures, $i = 1, \dots, n$. Let $Y_{ij} = 1$ if the j th procedure from individual i leads to a SHAE and let $Y_{ij} = 0$ otherwise, $j = 1, \dots, K_i$, $i = 1, \dots, n$. Let $X_i = 1$ if individual i is randomized to the experimental arm and $X_i = 0$ otherwise and let V_i be an additional covariate vector which includes indicators for the sites, and let $Z_i = (X_i, V_i)$. Let $\mu_{ij} = E(Y_{ij})$ denote the mean response for the marginal probability of a SHAE given the full covariate vector Z_i . The event rate is expected to be very low, so in order to estimate the relative risk, the log link function in a generalized linear model (McCullagh and Nelder, 2019) is used in the form of

$$\log \mu_{ij} = \beta_0 + \beta_1 X_i + \beta_2 V_i$$

where $\beta = (\beta_0, \beta_1, \beta_2)$ and the relative rate of a SHAE is $\exp(\beta_1)$ when adjusting for the covariates V_i . Analysis will be carried out based on quasi-likelihood with the identity variance function (Lumley et al, 2006).

The variance function is not the binomial variance function and the responses Y_{ij} , $j = 1, \dots, K_i$ corresponding to the SHAE responses for successive procedures from the same donor are not independent. Therefore, in order to provide protection against a) misspecification of the variance function and b) a working independence assumption for procedures from the same donor, analyses will be based on the generalized estimating equation approach (Liang and Zeger, 1986). A robust variance estimate will be used for inference by defining clusters based on a donor identification variable. Once the above log link model is fitted, the confidence interval approach will be used such that non-inferiority will be claimed if

$$\exp\left(\hat{\beta}_1 + 1.96 s.e.(\hat{\beta}_1)\right) < RR_M$$

where $s.e.(\hat{\beta}_1)$ is the square root of the robust variance estimate.

The following is the list of secondary parameters and how they will be analyzed. If any subgroup target number of donations has not been achieved after the overall sample size has been met, sites will be asked to continue to collect donations over an extended period of follow-up specifically for donors in the target subgroups who are already on-study, and to focus recruitment of new individuals to those of each target subgroup(s) until the minimum number of procedures is met for each subgroup. Each subject in any target subgroup may donate only during their 8-week participation period. If enrollment during the extension period for any of the subgroups is not sufficient to complete the study in a reasonable time period (defined as an extension period of up to 3 months), then the extension period could be stopped at the discretion of the sponsor.

1. Incidence rate of SHAEs per donor status (first-time)

Analysis will be carried out to estimate the relative risk of significant hypotensive events for first-time donors. First-time donors are defined as individuals who have not donated plasma in the preceding six months. Individuals retain their first-time status only for their first procedure during the study period. Since there is no clustering of responses, a simple robust variance estimate will be used to provide protection against misspecification of the

identity variance function. Once the model is fitted, a point estimate and a 95% confidence interval will be computed for the relative rate of SHAE for first time donors. With a relative rate for a SHAE = 1.2 and the non-inferiority margin of $RR_M = 4$, a sample size of $n = 1,329$ procedures is required for this subgroup to have 80% power.

2. Incidence rate of SHAEs for female donors

The log linear model stated above will be fitted for female donors with the same specifications as the primary analysis with a binary procedure-specific response: a log-link, identity variance function, and working independence assumption for procedures from the same donor. Once the model is fitted, a point estimate and a 95% confidence interval based on a robust variance estimate will be computed for the relative rate of SHAE for female donors. With a relative rate for a SHAE = 1.2 and the non-inferiority margin of $RR_M = 2.5$, a sample size of $n = 26,366$ procedures is required for this subgroup to have 90% power.

3. Incidence rate of SHAEs for donors ≤ 20 years of age

The log linear model stated above will be fitted for the subgroup of donors ≤ 20 years of age with the same specifications as the primary parameter analysis with binary procedure-specific response: log-link, identity variance function, and working independence assumption for procedures from the same donor. Once the model is fitted, a point estimate and a 95% confidence interval based on a robust variance estimate will be computed for the relative of SHAE for donors ≤ 20 years of age. With a relative rate for a SHAE = 1.2 and the non-inferiority margin of $RR_M = 4$, a sample size of $n = 2,514$ procedures is required for this subgroup to have 80% power.

4. Incidence rate of SHAEs for donors ≤ 124 lbs

The log linear model stated above will be fitted for the subgroup of donors weighing ≤ 124 lbs with the same specifications as the primary parameter analysis with binary procedure-specific response, log-link, identity variance function, and working independence assumption for procedures from the same donor. Once the model is fitted, a point estimate and a 95% confidence interval based on a robust variance estimate will be computed for the relative of SHAE for donors ≤ 124 lbs. With a relative rate for a SHAE = 1.2 and the non-inferiority margin of $RR_M = 4$, a sample size of $n = 4,827$ procedures is required for this subgroup to have 80% power.

5. Incidence rate of hypotensive severe/injury adverse events (IQPP DAE Classification 1.5 or 1.6)

The log linear model stated above will be fitted for the subgroup of donors to find the incidence rate of severe/injury hypotensive adverse events with the same specifications as the primary parameter analysis with binary procedure-specific response, log-link, identity variance function, and working independence assumption for procedures from the same donor. Once the model is fitted, a point estimate and a 95% confidence interval based on a robust variance estimate will be computed for the relative incidence rate of severe/injury hypotensive adverse events.

6. Time from start of plasmapheresis procedure to the first SHAE

For each procedure, the time (in minutes) from the start of plasmapheresis to the first SHAE will be recorded. For procedures not leading to a SHAE, the time will be censored at the time the plasmapheresis is completed. The cumulative incidence function for the time to the first SHAE for a procedure will be estimated for each arm of the study with a gamma distributed random effect used to accommodate a dependence in the time to a SHAE across procedures within the same donor. To estimate the effect of the device on the time to the first SHAE, a stratified Cox regression model will be fitted with a donor-specific gamma distributed random effect (with a mean of 1 and variance ϕ to be estimated) and treatment arm (Aurora Xi New Nomogram or the Aurora Xi Optimized Nomogram), with stratification by center. The exponentiated regression coefficient will give the hazard ratio for the time to the first SHAE per procedure.

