**Study Design:** This is a multicenter, prospective randomized controlled clinical trial to evaluate the Aurora Xi New Nomogram for the collection of plasma. The Test group will utilize the Aurora Xi Plasmapheresis system with New Nomogram (software version 2.0) and the Control group will utilize the Aurora Xi Plasmapheresis System with Optimized Nomogram (software version 1.3). Subjects will be retained in the assigned study arm (Test/Control) throughout their participation in the study period. Participants will donate for up to 8 weeks for the primary endpoint analysis, resulting in at least 51,720 plasmapheresis procedures. At that point, the primary endpoint analysis will take place. If noninferiority is demonstrated for the primary endpoint, but subgroup enrollment is not judged to be sufficient, an optional extension period will begin, during which collections and enrollment will continue from specific subpopulations (first-time donors, female donors, young donors, and low body weight donors). Collections performed during the optional extension period will not be included in the primary endpoint analysis but will be included for secondary endpoint analyses / subgroup analysis.

It is anticipated that enrollment will take approximately 6-9 months. Prior to enrollment, all subjects will be required to provide a signed informed consent for this research study and meet all standard requirements for the plasma collection center. Subjects will be considered enrolled at the time of venipuncture for the first on-study collection procedure. Plasmapheresis subject evaluations will be completed pre-procedure, during the procedure, and post-procedure between the date of the first on-study collection and up to 2 weeks after the last on-study collection.

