# 12 STATISTICAL METHODS AND SAMPLE SIZE

## 12.1 General Overview

All of the data will be verified and archived by Fresenius Kabi, USA, Lake Zurich, IL. Any change to the data analysis methods described in this protocol will require an amendment ONLY if it changes a principal feature of the protocol. Any change to the data analysis methods described in the protocol, and the justification for making the change will be described in the final study report.

The primary objective of this study is to demonstrate that the per procedure rate of significant hypotensive adverse events (SHAEs) using the Aurora Xi New Nomogram algorithm is less than double the SHAE rate under the Aurora Xi Optimized Nomogram algorithm. This is a multi-center randomized controlled trial in which plasma donors at three centers will be recruited and randomized in a 1:1 ratio to use the Aurora Xi New Nomogram algorithm or the Aurora Xi Optimized Nomogram algorithm.

Standard summary statistics (e.g., count, mean, standard deviation, minimum, median, and maximum values) will be reported for subject and procedure parameters.

One secondary objective is to demonstrate that the per procedure rate of severe hypotensive adverse events (IQPP DAE Classification 1.5 or 1.6) under the Aurora Xi New Nomogram algorithm is non-inferior to the per procedure severe hypotensive adverse event rate using the Aurora Xi Optimized Nomogram algorithm. Analyses will be carried out as in the primary analysis with this binary donation-specific response, log-link, identity variance function, and working independence assumption. A robust variance estimate will be used for inference to provide protection against a within-donor association in responses of successive procedures within clusters defined by donor identifying numbers.

The Statistical Analysis Plan will expand on the data analysis to be conducted for the remaining endpoints.

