### 12.4 Analyses

Standard summary statistics (e.g., number, mean, standard deviation, minimum, median, and maximum values) will be reported for subject and procedure parameters. Analyses will be performed to evaluate the primary objective to demonstrate that the per procedure rate of significant hypotensive adverse events (SHAEs) using the Aurora Xi New Nomogram algorithm is less than double the rate of SHAE rate under the Aurora Xi Optimized Nomogram algorithm in Section 12.2.

Additional analysis will be performed to demonstrate that the per procedure rate of severe hypotensive adverse events (IQPP DAE Classification 1.5 or 1.6) under the Aurora Xi New Nomogram algorithm is non-inferior to the per procedure severe hypotensive adverse event rate using the Aurora Xi Optimized Nomogram algorithm. Analyses will be carried out as in the primary analysis with this binary procedure-specific response, log-link, identity variance function, and working independence assumption. A robust variance estimate will be used for inference to provide protection against a within-donor association in responses of successive procedures with clusters defined by donor identifying numbers. The same non-inferiority margin will be used as for the primary response.

A detailed statistical procedure will be outlined in the Statistical Analysis Plan for the other secondary endpoints.

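### SAP 4.2 item 5 (severe/injury events, 1.5/1.6) has no rule for an arm with no events; if software reports that fit, the Wald rule claims non-inferiority from 0 Test v 1 Control

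*SAP*

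**What the plan says.** SAP 4.2 describes one model for the secondary rate comparisons: log link, variance equal to the mean, working independence, site indicators, and a sandwich variance clustered on donor. The decision rule is general: "Once the above log link model is fitted, the confidence interval approach will be used such that non-inferiority will be claimed if" exp(β̂₁ + 1.96 s.e.) is below RR_M.

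Item 5 applies this model to 1.5/1.6 events and says a "95% confidence interval based on a robust variance estimate will be computed for the relative incidence rate of severe/injury hypotensive adverse events". Item 5 gives no margin, event rate, sample size or power. The margin comes from Protocol 12.4: "The same non-inferiority margin will be used as for the primary response", that is, 2. Protocol 12.1 says the same of the model: "Analyses will be carried out as in the primary analysis with this binary donation-specific response, log-link, identity variance function, and working independence assumption".

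Of SHAEs of all grades (1.2 to 1.6), SAP 4.2 says: "The event rate is expected to be very low". The 1.5/1.6 events are a subset of these. Neither document has an exact, continuity-corrected, minimum-count or not-estimable rule. SAP 5.4.1 deals with missing data only. On software, SAP 3.3 states: "All calculations will be performed using SAS 9.4 (Windows platform)".

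**The concern.** When events are this rare, one arm may have none. With an empty Test arm the estimate of β₁ runs off to minus infinity, and a sound interval should then be very wide. The sandwich variance does the opposite, because an empty arm adds almost nothing to it. Software that stops iterating at some large negative β̂₁ prints a tiny standard error and an upper limit close to zero, and the written rule reads that as non-inferiority.

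The objective covers the most severe donor events in the trial. At stake is a non-inferiority claim on them that rests on a single Control event. If the software stops instead, the result is undefined and its handling would be chosen after the counts are known.

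**Working it through.** **Inputs.** 51,720 procedures at 1:1, so about 25,860 per arm (SAP 3.1). Control SHAE rate 0.00221 (SAP 3.1). Margin 2 (Protocol 12.4). Two-sided 95% interval (SAP 4.1). Expected Control SHAEs of all grades: 25,860 × 0.00221 = 57.15. *Assumption:* 1.5/1.6 events are 1, 2, 3, 5, 10 or 20% of these. The plan has no figure of its own for item 5 to reproduce.

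**Step 1: why the standard error stays small.** Under working independence, the robust variance of β̂₁ is roughly the sum over arms of (sum of squared donor residual totals)/(fitted events)². With b Control events in different donors, the Control arm gives about b/b² = 1/b. In an empty Test arm each donor's residual total is −μKᵢ, so that arm gives ΣKᵢ²/(ΣKᵢ)², which is near 0 whatever tiny μ the software stops at. Hence s.e. ≈ 1/√b.

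**Step 2: fits** (statsmodels GEE, log link, variance equal to the mean, independence, donor clusters):
- 0 Test v 1 Control: β̂₁ = −22.386, robust s.e. 1.000, upper limit exp(−22.386 + 1.96) = 1.3 × 10⁻⁹. Reported as converged, no warning.
- 0 v 2: upper limit 7.6 × 10⁻¹⁰. 0 v 3 with site terms: 2.2 × 10⁻¹⁰.
- 1 Test v 0 Control: upper limit above 10⁸, so no claim. 0 v 0: the fit stopped with an error.
- 6 v 6 with site terms: 3.10, matching exp(1.96 √(2/6)).

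The model-based s.e. for 0 v 1 is about 72,700, so the false precision comes from the sandwich.

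**Step 3: exact limits.** Conditioning on total events with equal procedures, the exact upper limit for 0 v b is 0.025^(−1/b) − 1: 39 for b = 1, 5.3 for b = 2, 2.42 for b = 3, 1.51 for b = 4. At least 4 Control events are needed before an empty Test arm supports a ratio below 2.

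**Step 4: error rates.** Independent Poisson counts a (Test) and b (Control). The Wald limit is (a/b) exp(1.96 √(1/a + 1/b − 2/25,860)) when both are positive. *Written rule:* 0 v ≥1 counts as a claim, as statsmodels would give. *Exact fallback:* when a = 0, claim only if the exact limit is below 2. There is no claim when b = 0 under either rule. Worked cell: at 0.57 expected Control events and true RR 2, the empty-Test cell alone gives e^(−1.143) × (1 − e^(−0.5715)) = 0.319 × 0.435 = 13.9%.

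| Share of SHAEs | Expected Control events | False claims at RR 2: written, fallback | Success at RR 1: written, fallback | An arm empty at RR 1 |
|---|---|---|---|---|
| 1% | 0.57 | 13.9%, 0.1% | 24.6%, 0.2% | 81% |
| 2% | 1.14 | 7.1%, 0.5% | 22.0%, 1.2% | 54% |
| 3% | 1.71 | 3.4%, 1.0% | 16.1%, 3.0% | 33% |
| 5% | 2.86 | 2.3%, 2.1% | 11.8%, 8.2% | 11% |
| 10% | 5.72 | 2.5%, 2.5% | 21.7%, 21.6% | 0.7% |
| 20% | 11.43 | 2.6%, 2.6% | 37.9%, 37.9% | 0.0% |

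The written rule returns to 2.5% at about 2.1 expected Control events (2.1/57.15 = 3.7% of Control SHAEs).

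**Step 5: the one related figure.** Protocol 12.10 Rule 2 triggers DSMB review at 6 or more 1.5/1.6 events in the first half of procedures. At RR 1 the pooled expected count in that half equals the expected count per arm over the whole trial. The chance of 6 or more is therefore about 7% at 2.86 and 51% at 5.72.

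**The case against.** The strongest reply is that the false claim has not been shown in the plan's own software. SAS 9.4 may warn or stop, and the rule applies only once the model is fitted, so on paper the case is undefined rather than wrongly decided. That stands, and it limits the finding to a conditional one. The gap remains either way, since the SAP does not say what is reported if the fit fails.

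Second, inflation needs fewer than about 2.1 expected Control events, and no document puts the trial there. That also stands. The DSMB trigger is compatible with a low rate, since a trigger meant to be exceptional would otherwise fire often, but it does not settle the rate. Collections in the optional extension "will be included for secondary endpoint analyses / subgroup analysis", which could raise the counts somewhat.

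Third, the consequence is small. SAP 3.3 says "Summary statistics (e.g., counts and percentages) will be reported on categorical (non-numeric) parameters for each randomization group", so a reader would see 0 v 1. No section makes item 5 a condition of study success, and severe events have their own unblinded DSMB review. All of this is correct and is why the point is graded low.

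A reader might infer that the robust Wald rule is unsound for item 5 in general, or that the primary analysis shares the fault. Neither follows. With events in both arms the rule holds about its level, and the primary endpoint expects about 57 Control events.

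**Conclusion.** The gap is real and minor. Item 5 applies a Wald rule to the rarest events in the trial without providing for an empty arm. Taken literally on software that reports the fit, the rule claims non-inferiority from 0 v 1. False claims at a true relative rate of 2 would then be 3.4 to 13.9% in the three lowest scenarios and about nominal from 2.86 expected Control events up.

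This rests on an assumed 1.5/1.6 rate, independent Poisson counts, equal procedures per arm, and software that behaves as statsmodels does. It does not show that SAS 9.4 would print such a limit, nor that the severe rate is in fact that low. The harm is confined to one secondary claim.

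**What to change.** Keep the site-adjusted GEE rule unchanged when both arms have events. Add to SAP 4.2 item 5:

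> If either arm has no events, whatever the software reports, the GEE limit will not be used. Counts per arm, the number of donors contributing the events, and an exact conditional 95% confidence interval for the rate ratio will be reported. Non-inferiority will be claimed only if the exact upper limit is below 2 (with an empty Test arm and equal procedures, at least 4 Control events). If Control has no events, no claim is made.

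The trigger must be the event count, because the convergence flag did not detect the problem.

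The cost is one SAP paragraph and a few lines of code, with no protocol change. There are two downsides. The exact interval ignores site and donor clustering: four Control events from fewer than four donors would still pass at 1.51, which is why the donor count is reported. Success at RR 1 also falls where events are very few, including from 11.8 to 8.2% at 2.86 expected events, where the written rule was not inflated. The claims lost are those from 0 v 1, 0 v 2 and 0 v 3.

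A simpler alternative is to report the ratio as not estimable and make no claim whenever an arm is empty. It needs no independence assumption. Success at RR 1 is then 6.4% at 2.86 and 21.4% at 5.72 expected events. Either rule closes the gap if fixed before the counts by arm are known.
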